13.0 CRITERIA FOR REMOVAL FROM STUDY

Off-therapy Criteria

Patients with medically concerning grade 3 or 4 adverse events related to drug therapy may be taken off therapy at the discretion of the principal investigator.

- Patients who require more than 2 dose reductions of carfilzomib
- Hematologic toxicity has not completely resolved or resolved to < grade 1 or baseline after 2 weeks of withholding treatment
- Therapy has been held for more than 3 weeks due to treating a grade 3 infection
- Grade 4 non-blistering rash or blistering rash of any grade
- Grade 4 neuropathy
- Grade 4 hypersensitivity reaction
- Patient experiencing significant cardiac event as outlined in section 9.5

- Patient completes the protocol treatment
- Progression of disease
- Patient chooses to go off therapy
- The principal investigator may remove patient from protocol therapy if deemed necessary due to medical conditions, compliance, etc.
- Patient becomes pregnant.

Off-Study Criteria

- Patient requests to be withdrawn from study
- Death
- Physician's determination that withdrawal is in the patient's best interest.

Patient has completed 1- and 3-year evaluation from end of therapy

14.0 BIOSTATISTICS

Phase I:

The goal of the phase I trial is to find the maximum tolerated dose (MTD) of carfilzomib when used in combination with lenalidomide and dexamethason. The trial design is a standard 3 by 3 dose escalation design. The three carfilzomib dose levels that will be explored are listed in Section 4.2.2 and the DLT evaluation window is the first cycle of therapy. The DLT definition is provided in Section 4.2.1.

1. A cohort of three patients will be enrolled at the first dose level (45/mg/m²). If no DLTs are observed in the cohort, the next dose level will be explored.
2. If one DLT is observed in the initial cohort of three, an additional three patients will be treated at the same dose level. If no additional patients have a DLT, the next dose level will be explored.
3. If at any point two or more patients have a DLT at a given dose level, the MTD will have been exceeded and the previous dose level will need to be investigated.
4. If three patients are treated at a potential MTD, the dose cohort will be expanded to six for confirmation.

Using this dose escalation scheme, escalation to the next treatment level is probable if the risk of DLT is low, and the likelihood of escalations decreases as the risk of DLT increases, as demonstrated in table below:

Table Dose Escalation/Toxicity Risk

| | | | | | | |
|---------------------------|-----|-----|-----|-----|-----|-----|
| True risk of Toxicity | .10 | .20 | .30 | .40 | .50 | .60 |
| Probability of Escalation | .91 | .71 | .49 | .31 | .17 | .08 |

The minimum and maximum sample size for the phase I trial is 4 and 18, respectively. It is anticipated that 1-2 patients per month may enroll on this trial; thus, approximately one year or less is anticipated as the accrual period for the phase I study.

Phase II:

The phase II component of this trial will explore the efficacy of the combination therapy using the carfilzomib dose selected in the phase I trial. The primary endpoint is CR/sCR MRD negativity (MRD-) rate by flow cytometry upon or prior to completion of 12 cycles of therapy. Patients with <CR/sCR are considered MRD positive. Based on previous research an CR/sCR MRD- rate by flow cytometry of 45% would be promising enough to warrant further investigation, while a rate of 20% would not be promising for further investigation. Using a Simon's optimal two-stage design, the first stage of the trial will enroll 14 patients. This includes the three-six patients treated at the MTD in the phase I trial. If three patients or fewer are CR/sCR MRD- by flow cytometry, the trial will stop due to a lack of efficacy; otherwise, an additional 11 will enroll to a total sample size of 25 at end of phase II. If at least eight patients are MRD- (at the MTD), the intervention will be considered promising for further research. The type I error is set at 0.10 and the type II error is set at 0.10. If the true MRD-rate is 20%, the probability of early termination is 70%. For patients that come off trial prior to completion of 4 cycles of therapy, due to reasons unrelated to disease progression or toxicities, patients can be replaced (max 3) for MRD evaluation as part of the phase II assessment.

It is anticipated that 1-2 patients per month may enroll on this trial; thus, approximately one year is anticipated as the accrual period for the phase II study. The total maximum possible projected sample size for the study is 37 patients.

Secondary endpoints for both Phase I and II:

1. To estimate the overall response rate (ORR) according to International Myeloma Working Group criteria at each cycle and as the best response during the treatment of up to 12 cycles. In addition to ORR, the rates of VGPR+CR and CR alone will also be estimated and reported. The exact 95% confidence intervals will also be included.
2. Kaplan-Meier methodology will be used to estimate progression-free survival and overall survival. Estimates of survival along be with 95% confidence intervals will be provided for select time points.
3. To explore the concordance of different MRD methodologies. MRD status by multiparametric flow cytometry will be compared to next-generation sequencing and to mass spectrometry based proteomics methodologies. The concordance across the different technologies will be reported along with an exact 95% confidence interval.
4. To create a bone marrow and peripheral blood sample bank. These samples may be used to later evaluate the biological activity of carfilzomib, lenalidomide, and dexamethasone. Potential analyses include sequencing and gene expression profiling on pre and post therapy bone marrow samples, identification of potential biomarkers (blood, urine, bone marrow aspirates), and evaluation of proteasome activity.

Exploratory Studies:

1. The gene panel HemePACT (or alternative equivalent platform) will explore whether any mutations appear to be associated with response to therapy or toxicity associated with therapy. This descriptive aim will combine patients across all dose levels. This analysis is for hypothesis-generation, and all results will be cautiously interpreted. Fisher's exact test

may be used to assess any potential association. The variant allele frequency (VAF) will be summarized for each mutation.

2. HemePACT (or alternative equivalent platform) will also be evaluated using samples at the time of progression of disease or during an ongoing response and will be compared to the pre-treatment baseline samples to explore whether pathways leading to emergence of resistance to the drug regimen can be identified. Similar to the previous objective, this aim is for hypothesis generation, and all results will be cautiously interpreted. Changes in the VAF from baseline will be summarized for patients with an ongoing response and for patients who have progression of disease. A paired t-test may be used to further describe this association. This aim will combine patients across all explored dose levels.

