At the National Cancer Institute, we recently published results of a phase II clinical and correlative study of CRd in patients with newly diagnosed MM patients¹{Korde, 2015 #4573}. Patients were administered eight 28-day cycles of therapy including carfilzomib IV 20/36 mg/m² (based on prior Jakubowiak trial) on days 1, 2, 8, 9, 15, 16. After 8 cycles of CRd, all patients with stable disease (SD) or better receive cycles 9–20 of lenalidomide

maintenance 10 mg days 1–21. Of the 45 patients evaluable for toxicity and response, none reported \geq grade 3 neuropathy. This finding stands in sharp contrast with bortezomib, which can be associated with sensory neuropathy in up to 80% of treated patients when used in combination with lenalidomide and dexamethasone¹³. The CRd regimen (using 36 mg/ m²) resulted in rapid and deep responses with an overall response rate of 98% (n=42) and sCR/CR in 56% (n=25). The median time to sCR was 5 cycles (range 2-18).

Minimal Residual Disease Testing in Myeloma

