In the past decade, multiple myeloma patients have reached deeper response rates with use of effective anti-myeloma therapeutics, immunomodulatory agents and proteasome inhibitors, approximating up to 75% patients achieving near-complete response (>90% decrease in monoclonal protein) or complete response (100% decrease in monoclonal protein){Kumar, 2008 #716}. In general, improved therapeutics and deeper response rates have resulted in improved overall survival of multiple myeloma patients across most age groups. As a result, there has been an increasing demand for the development of sensitive assays to detect minimal residual disease (MRD) in treated MM patients. In MM patients receiving autologous stem cell transplant, MRD-negative status using multi-parametric flow cytometry (MFC) is associated with improved progression free survival and overall survival. Similar studies using next generation sequencing methods for MRD have also been shown to be associated with improved outcomes in MM MRD-negative patients. In our prior study, among the 25 patients with CR/sCR that were assessed by MFC for immunophenotypic abnormal plasma cells; 25 out of 25 were negative for (MRD with an overall MRD negative rate of 25/43 (58%) (*2 patients did not have evaluable samples) using MFC. Using next generation sequencing molecular tests, the CR/sCR MRD negative rate was 13/33 (39%) (*12 patients did not have evaluable samples) (Sequenta platform). In patients with NDMM treated with CRd, 12-month progression-free survival for MRD-negative vs MRD-positive status by flow cytometry and next-generation sequencing was 100% vs 79% (95% CI, 47%-94%; $P < .001$) and 100% vs 95% (95% CI, 75%-99%; $P = .02$), respectively.

Minimal Residual Disease Platforms

A recent survey including 30 major institutions in the US found major heterogeneity in MRD testing of multiple myeloma by flow cytometry¹⁶. In brief, there was considerable variation in the number of bone marrow cells analyzed (events) and number of abnormal plasma cells needed to define the presence of MRD, which affects maximum possible sensitivity. The maximum detection sensitivity ranged from 0.0005% to 0.02%, a 100-fold difference in sensitivity. Also, the variation in antibodies studied and definition of an abnormal plasma cell by flow cytometry affected the ability to differentiate normal from neoplastic plasma cells.

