3.2 Proposed Study Investigation with Correlative Studies

Given the potent anti-myeloma activity of the CRd combination as demonstrated by rapid and deep remissions and the lack of a defined MTD, as a logical extension to the above mentioned studies, we propose a phase I/II investigation in newly diagnosed MM employing 2 escalated dose levels of carfilzomib at 20/45mg/m² and 20/56mg/m² in combination with lenalidomide and dexamethasone administered over a maximum 12 twenty-eight day cycles. These two dose levels were chosen based on information provided by Amgen Pharmaceuticals and based on phase 1 studies in relapsed-refractory MM showing the safety and efficacy of the drug as well as evidence of a dose-response relationship on multivariate modeling analysis¹⁷⁻¹⁹.

After 4 cycles of treatment with CRd, transplant eligible patients will be encouraged to undergo autologous stem cell harvesting. Harvested stem cells will be stored for future use at time of disease relapse or progression. All patients will receive combination therapy with CRd. M-spikes and FLCs will be monitored every month. Patients achieving ≤PR after completion of 4 cycles of therapy will stop protocol therapy. Patients that are <CR/sCR (but >PR after 4 completed cycles) will receive up to 12 cycles of CRd. At any point during protocol, if patients achieve CR/sCR by serum and/or urine assessments²⁰, patients will undergo bone marrow biopsy to confirm CR per standard criteria. At work-up, if the bone marrow is found to be MRD negative by multiparametric flow cytometry, patient will receive 2 additional cycles of CRd (maximum 12 cycles). Patients that are CR/sCR but MRD positive by multiparametric flow cytometry will receive 12 cycles of CRd. The first pulled bone marrow sample will be sent for multi-parametric flow cytometry as a priority sample. Upon completion of protocol therapy, patients will be encouraged to proceed onto maintenance therapy or high dose therapy with stem cell rescue under a separate treatment protocol or standard of care. Some patients may need alternative therapy after completing protocol therapy. Collected bone marrow and peripheral blood samples will be processed and stored to create a sample bank used to later evaluate biological activity of carfilzomib, lenalidomide, and dexamethasone.

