7.0 RECRUITMENT PLAN

This study will be conducted at MSKCC. Efforts will be made to ensure that women and minority groups are adequately represented in this trial. Internally, an effort will be made to position this protocol for patients that demonstrate high-risk prognostic features, so as not to conflict with other ongoing newly-diagnosed multiple myeloma studies. All patients will be seen by MSKCC myeloma physicians and associated MSKCC co-investigators, enrolled and registered at MSKCC. All co-investigators agree to follow the treatment in the protocol and to conduct the proposed investigation according to recognized principles of good clinical practice. Participation is voluntary. Each patient must be informed about the neoplastic nature of his/her disease and willingly consent to participation in this study. Every patient will be informed of the procedures to be followed, the potential benefits, side effects, risks, and discomforts of the trial and of potential therapeutic alternatives. All participants will be required to sign statements of informed consent and research authorization that conform to FDA, IRB and HIPAA guidelines. Informed consent will be documented by the use of a written consent form that has been approved by the MSKCC IRB.

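### Do the 20% and 45% MRD-negativity targets need resetting against the 58% reported for the earlier carfilzomib, lenalidomide and dexamethasone study?

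*Combined protocol and SAP*

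**What the plan says.** The Phase II part of Section 14.0 takes as its primary endpoint MRD negativity by flow cytometry, in patients with CR or sCR, by the end of 12 cycles. Patients short of CR count as MRD positive. The upper target is introduced with "Based on previous research an CR/sCR MRD- rate by flow cytometry of 45% would be promising enough to warrant further investigation". The lower target, the rate treated as not worth pursuing, is 20%. A Simon optimal two-stage design enrols 14 patients, stops at three or fewer successes, and otherwise continues to 25. The final rule is "If at least eight patients are MRD- (at the MTD), the intervention will be considered promising for further research". Both error rates are set at 0.10, and early termination at a true rate of 20% is given as 70%.

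For the overall, VGPR-plus-CR and CR rates, the secondary analyses state "The exact 95% confidence intervals will also be included". Assay concordance also gets an exact interval. None is stated for the primary rate.

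Section 3.1 describes an earlier study of the same combination in newly diagnosed patients at carfilzomib 20/36 mg/m². Its flow result in the CR/sCR patients is reported as "25 out of 25 were negative for (MRD with an overall MRD negative rate of 25/43 (58", the last figure being a percentage. Two further patients had no evaluable sample. Section 3.2 presents the present trial in these terms: "as a logical extension to the above mentioned studies, we propose a phase I/II investigation in newly diagnosed MM employing 2 escalated dose levels".

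**The concern.** The combination is the same, carfilzomib is escalated, and the only flow-MRD rate the protocol gives for it is 58%. Both design rates lie below that figure and Section 14.0 does not say why. A result of 8/25 would be labelled promising although 32% is below the lower confidence limit of the earlier result. If the label were read as evidence that escalation helps, it would mislead, and no planned interval on the primary rate would correct the reading. Passing also becomes close to certain if the regimen merely repeats the earlier result, so the rule cannot tell 45% from 58%.

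**Working it through.** **Inputs.** From Section 14.0: n1 = 14, stop at 3 or fewer; n = 25, success at 8 or more; p0 = 0.20, p1 = 0.45. From Section 3.1: 25/43 by flow with 2 not evaluable, so 25/45 if those count as failures; and 13/33 by next-generation sequencing in the same cohort, with 12 not evaluable.

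**1. The plan's own figures.** With true rate p,

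P(stop early) = P(Bin(14, p) ≤ 3)

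P(pass) = Σ over x = 4 to 14 of P(Bin(14, p) = x) × P(Bin(11, p) ≥ 8 − x)

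| True rate | P(stop early) | P(pass) |
|---|---|---|
| 20% | 0.698 | 0.093 |
| 35% | 0.220 | 0.638 |
| 40% | 0.124 | 0.798 |
| 45% | 0.063 | 0.903 |
| 55.6% (25/45) | 0.010 | 0.987 |
| 58.1% (25/43) | 0.006 | 0.993 |

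The stated 70% early termination and both 0.10 error limits are reproduced. A search over two-stage designs confirms this as the optimal one for 20% against 45%, with expected sample size 17.3 at 20%.

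**2. What a bare pass shows.** 8/25 = 32%. The Clopper-Pearson 95% interval is 14.9% to 53.5%. Allowing for the two stages, with early stops ranked lowest, it is 15.4% to 54.8%, and the one-sided 90% lower bound is 20.3%. So a bare pass excludes 20% at one-sided 10%, and no more. At 9/25 the ordinary 95% interval (18.0% to 57.5%) still contains 20%; at 10/25 it starts at 21.1%.

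**3. The earlier result.** 25/43 = 58.1%, exact 95% interval 42.1% to 73.0%. 25/45 = 55.6%, interval 40.0% to 70.4%. The target of 45% is inside both; 32% is below both. Two-sided Fisher tests:

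| New result | against 25/43 | against 25/45 |
|---|---|---|
| 8/25 | 0.047 | 0.081 |
| 9/25 | 0.131 | 0.140 |

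So even at the boundary, a worse result than before is suggested but not established.

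**4. How often a pass would be low.** The share of passes that come from 8 to 10 successes is P(pass with 8–10) / P(pass):

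- true rate 40%: 0.387 / 0.798 = 48%
- true rate 45%: 0.290 / 0.903 = 32%
- true rate 55.6%: 0.0754 / 0.987 = 7.6%
- true rate 58.1%: 0.0460 / 0.993 = 4.6%

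If the regimen performs as the earlier one did, a low pass is rare. In addition, 10/25 = 40.0% falls below the 25/43 limit (42.1%) but not below the 25/45 limit (39.997%).

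**5. Sensitivity of the benchmark to the assay.** Sequencing in the same earlier cohort gave 13/33 = 39% (exact 95% interval 22.9% to 57.9%). Against that figure, 8/25 gives Fisher p = 0.59. The evaluable sets differ and sequencing is not this trial's primary assay, so this does not bound the effect of the new 10-color flow platform. It does show that an MRD-negative rate is not fixed across methods.

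**The case for a change.** The strongest argument for a change is that the differences between the studies may explain 45% but not 20%. Section 3.1 says "The median time to sCR was 5 cycles (range 2-18" for the earlier study. If that median applies to all 25 responders, at least 13 had responded by cycle 5, and 13/45 = 29%, already above 20%. The 12-cycle window therefore cannot account for the lower target by itself. This stands as far as it goes, but it needs a second assumption, that those patients were also MRD negative by then, and the protocol does not say when the earlier MRD samples were taken. More importantly, 20% is the rate at which the investigators would lose interest; it is not a forecast. Other differences also push downwards by amounts the documents do not give: removal at PR or worse after cycle 4, a different flow platform, and the recruitment plan's statement that "an effort will be made to position this protocol for patients that demonstrate high-risk prognostic features".

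A second argument is that the pass label should rest on a comparison with 25/43. No criterion is available for that comparison and its confounders cannot be sized. It would replace a prespecified rule of known error rates with a judgement made after the data are seen. Resetting the targets within 25 patients, for example 45% against 70%, needs a 70% that no document supplies. It would cut early stopping at the null from 0.70 to 0.34, and would pass a regimen as good as the earlier one (56% to 58%) only 41% to 51% of the time.

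What remains is that Section 14.0 cites no source for its targets and states no interval for the primary rate. Both are true.

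**Conclusion.** No change to the plan is needed. The rule does what Section 14.0 says it does, and the claim attached to a pass is modest: further research is worthwhile. Choosing a low-bar activity screen for 25 patients is a fair trade-off, and 45% is compatible with the earlier data. The limitation is one of interpretation: 8/25 supports a rate above 20% at one-sided 10%, and any comparison with 25/43 is descriptive only.

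The gaps are ones an analyst fills as a matter of course. The phase II objective is to assess the MRD-negative rate, so a report would give that rate with an exact interval, preferably one allowing for the two stages, and would set the source of the targets and the differences between the studies beside it. None of this alters patient numbers or cut-offs.

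This conclusion assumes that the pass label is not presented as evidence of parity with or improvement on the earlier regimen. It also assumes that the unquantified differences in assay, window, early removal and case mix are large enough to make 25/43 unsuitable as a formal benchmark; the documents support their existence but not their size.

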Carfilzomib (Cfz) is a tetrapeptide ketoepoxide-based irreversible inhibitor that forms a covalent bond with N-terminal threonine residue of the chymotrypsin domain. Compared to bortezomib, carfilzomib demonstrates equal potency but greater selectivity for the chymotrypsin activity site over the tryptic and caspase domains. Also, carfilzomib is less reactive to non-proteasome proteases compared to bortezomib, likely contributing to lower levels of neuropathy and myelosuppression⁶⁻⁸. In vitro models suggest carfilzomib has activity against bortezomib resistant myeloma cell lines⁷. Carfilzomib can also work synergistically with dexamethasone to enhance tumor cell death⁷. In the pivotal, phase II, noncomparative study of heavily pre-treated patients (n=266) with relapsed and refractory multiple myeloma, intravenous carfilzomib administered in 28-day cycles for up to 12 cycles produced an overall response rate of 23.7% in the response-evaluable patients⁹. The median duration of response was 7.8 months, the median progression-free survival was 3.7 months and the median overall survival was 15.6 months. An integrated analysis of 3 phase 2 studies with single-agent carfilzomib in patients with relapsed and refractory myeloma (N = 526) showed that the most common grade 3/4 adverse events (AEs) were thrombocytopenia (23%), anemia (22%), and lymphopenia (18%); peripheral neuropathy was 14% for any grade and 1.3% for grade 3 with no grade 4 events¹⁰.

Carfilzomib in Combination with Lenalidomide and Dexamethasone

More recently, Jakubowiak et al published the results of a Phase 1/2 study in patients with newly diagnosed multiple myeloma where carfilzomib was administered in combination with lenalidomide (Revlimid®) and dexamethasone (CRd)¹¹. No maximum tolerated dose (MTD) was reached. The maximum planned dose level (carfilzomib 36 mg/m²) was expanded in phase 2 (n = 36). Grade 3/4 toxicities included hypophosphatemia (25%), hyperglycemia (23%), anemia (21%), thrombocytopenia (17%), and neutropenia (17%); peripheral neuropathy was limited to grade 1/2 (23%). After a median of 12 cycles (range, 1-25), 62% (N = 53) achieved at least near-complete response (nCR) and 42% stringent CR (sCR). Responses were rapid and improved during treatment. In 36 patients completing 8 or more cycles, 78% reached at least near CR and 61% stringent CR. With median follow-up of 13 months (range, 4-25 months), 24-month progression-free survival estimate was 92%.

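### Does Section 14 need an interval for the primary MRD-negative rate, given that an exact 95% interval would include 20% at 8/25 and 9/25?

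*Combined protocol and SAP*

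**What the plan says.** Section 14.0, Phase II, describes a Simon optimal two-stage design. Fourteen patients enter first. The trial stops if three or fewer are MRD-negative in CR/sCR; otherwise 11 more enter, making 25. The final rule is "If at least eight patients are MRD- (at the MTD), the intervention will be considered promising for further research". The two reference rates are "Based on previous research an CR/sCR MRD- rate by flow cytometry of 45% would be promising enough to warrant further investigation" and "while a rate of 20% would not be promising for further investigation". The error rates follow: "The type I error is set at 0.10 and the type II error is set at 0.10". The section also gives a 70% probability of early termination at a true rate of 20%, and allows up to three replacements for patients who leave before completing four cycles for reasons other than progression or toxicity.

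Intervals appear only under the heading for secondary endpoints. For the response rates, "The exact 95% confidence intervals will also be included". For the comparison of MRD methods, "The concordance across the different technologies will be reported along with an exact 95% confidence interval". Progression-free and overall survival get Kaplan-Meier estimates with 95% intervals. No interval, level or method is named for the primary rate there or anywhere else in the document.

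**The concern.** The phase II objective in Section 2.0 is to assess a rate, so a reader expects the final report to give that rate with an interval. The plan sets one for each secondary rate and none for the primary. The natural step would be to carry over the exact 95% method. At the two lowest passing counts the report would then call the regimen promising beside an interval that contains the rate described as not promising.

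The choice of interval also matters numerically at the boundary. For 8/25 the lower limit can fall on either side of 20%, depending on the level and on whether the first-stage stop is taken into account. An analyst choosing after seeing the data could make a marginal pass look firmer or weaker.

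A related doubt is that Section 14 credits 20% and 45% to earlier research without showing how they were derived. The carfilzomib-lenalidomide-dexamethasone results in Section 3.1 are 42% sCR, 56% CR/sCR, 58% MRD-negative by flow (25/43) and 39% by sequencing (13/33). None is near 20%.

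**Working it through.** **Inputs (Section 14.0).** First stage 14 patients, stop at 3 or fewer; total 25, pass at 8 or more; reference rates 0.20 and 0.45; both error rates 0.10.

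**1. The plan's own figures.** With X1 ~ Bin(14, p) and X2 ~ Bin(11, p):

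- Early stop = P(X1 ≤ 3). At p = 0.20 this is 0.044 + 0.154 + 0.250 + 0.250 = 0.698, against a stated 70%.
- Pass = Σ over k = 4 to 14 of P(X1 = k) × P(X2 ≥ 8 − k). At p = 0.20 this is 0.0933, and at p = 0.45 it is 0.9026.

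A full search over two-stage designs with both error rates at most 0.10 returns the same design as the optimal one, with expected size 17.3 at p = 0.20. The stated design reproduces.

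**2. Exact 95% (Clopper-Pearson) interval, if carried over to the primary rate.**

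| Result | Rate | 95% interval | Contains 20%? |
|---|---|---|---|
| 8/25 | 32% | 14.9% to 53.5% | yes |
| 9/25 | 36% | 18.0% to 57.5% | yes |
| 10/25 | 40% | 21.1% to 61.3% | no |

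Only 8 and 9 are affected.

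**3. Why the interval and the rule differ.** The rule allows 0.10 in one tail; a 95% interval allows 0.025. The two-stage one-sided p-values against 20% are 0.0933 at 8/25, 0.0433 at 9/25 and 0.0168 at 10/25. The first two lie between 0.025 and 0.10, so the rule passes them while a 95% interval keeps 20%. The third is below both limits.

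**4. An interval matched to the rule.** With 10% in each tail (an 80% interval), the lower limit at 8/25 is:

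- 19.6% if the stages are ignored, because the single-stage tail P(X ≥ 8 | 25, 0.20) is 0.109, above 0.10;
- 20.3% with stage-wise ordering, because the two-stage tail is 0.0933, below 0.10.

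At 9/25 these limits are 23.0% and 23.4%. Once level and stages both match the rule, interval and verdict agree. A stage-wise 95% interval still includes 20% at both counts (15.4% to 54.8% and 18.2% to 57.9%).

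**5. How often these counts occur.** P(8 or 9 of 25) is the probability of passing at 8 minus the probability of reaching 10:

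- true rate 20%: 0.0933 − 0.0168 = 0.0765;
- true rate 45%: 0.9026 − 0.7487 = 0.1539;
- true rate 58%, the flow result in Section 3.1: 0.9925 − 0.9753 = 0.0172.

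**The case for a change.** The case for a change is that the primary rate is the main quantity of the trial, that the right interval is not obvious, and that one 8/25 result can be given a lower limit of 14.9%, 19.6% or 20.3%. A sentence fixing the method in advance would cost almost nothing. At a true rate of 20%, the two affected counts make up 0.0765 of the 0.0933 chance of a false pass, which is 82%.

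The omission is real and the three limits are correct. The rest carries less weight. False passes cluster at the lowest passing counts under any discrete rule, and the 0.0765 lies inside the 0.10 that the plan openly accepts. Whichever limit is reported, the count alone decides the verdict.

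Naming a matched 80% interval alongside a descriptive 95% one would keep the apparent disagreement on the page. The agreement at 8/25 is also narrow, 20.3% against 20%, and assumes exactly 14 + 11 evaluable patients. If, as an assumption, one replaced patient stayed in the denominator as a second-stage patient, 8/26 would have a stage-wise 80% lower limit of 19.7%.

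The doubt about 20% and 45% shows no error either. A rate too low to pursue need not sit near results already seen, and 45% lies among the background figures. Those figures mix sCR, CR/sCR, flow and sequencing. Some features of this trial could lower its rate: recruitment aimed at high-risk patients, and stopping at PR or worse after four cycles. Others could raise it: higher carfilzomib dose levels, and up to 12 cycles of the combination where the earlier study gave eight.

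**Conclusion.** No change is called for. Section 14 gives the primary endpoint a valid decision rule whose stated error rates and early-stopping probability reproduce, and it claims only that a pass justifies further research. The conflict arises from applying to the primary endpoint a 95% interval that the plan reserves for secondary endpoints. Even then, a two-sided 95% interval containing 20% at 8/25 or 9/25 does not contradict a one-sided test at 0.10.

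The effect is confined to those two counts, with a probability of 15% at the design rate of 45% and 1.7% at 58%. In neither case does the verdict, an error rate or the sample size change. What remains is a reporting gap that an analyst can fill sensibly: give the observed rate with an exact interval that respects the two stages, state its level, and note that the count rule decides. The source of the 20% and 45% is likewise a matter of documentation.

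These figures assume exactly 25 evaluable patients, 14 and then 11; the replacement allowance is not modelled beyond the single 8/26 illustration.
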